#### **7.2.4 Immediate Reporting of Adverse Events to the Sponsor, Merck and Exelixis**

**All SAE must be recorded on a MedWatch 3500 Form. SAE reports and any other relevant safety information are to be forwarded to**

**Merck Global Safety**  
**[contact]**

**Exelixis**  
**[contact]**

MedWatch 3500 Reporting Guidelines:

*Note: MedWatch 3500 forms and other information related to MedWatch reporting are available at <http://www.fda.gov/medwatch/index.html>.*

All 15 Day Reports and Annual Progress Reports will be submitted by the sponsor as required by FDA. Investigators will cross reference this submission according to local regulations to the Merck Investigational Compound Number (IND, CSA, etc.) at the time of submission. Additionally investigators will submit a copy of these reports to Exelixis ([contact]-

[name]) and Merck & Co., Inc. (Attn: Worldwide Product Safety; [contact]) at the time of submission to FDA.

#### **7.2.4.1 Events of Clinical Interest**

Serious adverse events attributed to investigational agent as detailed in section 5.3.1 and 5.3.2 must be reported within 24 hours to the Sponsor and within 2 working days to Exelixis ([contact]) and Merck Global Safety. (Attn: Worldwide Product Safety; [contact]).

For the time period beginning when the consent form is signed until treatment allocation/randomization, any ECI, or follow up to an ECI, that occurs to any subject must be reported within 24 hours to the Sponsor and within 2 working days to Exelixis and Merck Global Safety if it causes the subject to be excluded from the trial, or is the result of a protocol-specified intervention, including but not limited to washout or discontinuation of usual therapy, diet, placebo treatment or a procedure.

For the time period beginning at treatment allocation/randomization through 90 days following cessation of treatment, or 30 days following cessation of treatment if the subject initiates new anticancer therapy, whichever is earlier, any ECI, or follow up to an ECI, whether or not related to Exelixis and Merck product, must be reported within 24 hours to the Sponsor and within 24 hours to Exelixis and Merck Global Safety.

#### **7.2.5 Evaluating Adverse Events**

An investigator who is a qualified physician will evaluate all adverse events according to the NCI Common Terminology for Adverse Events (CTCAE), version 4.0. Any adverse event which changes CTCAE grade over the course of a given episode will have each change of grade recorded on the adverse event case report forms/worksheets.

All adverse events regardless of CTCAE grade must also be evaluated for seriousness.

### **7.3 Reporting Requirements for IND holders**

For Investigator-sponsored IND studies, reporting requirements for the FDA apply in accordance with the guidance set forth in 21 CFR, Part 312.32. Events meeting the following criteria need to be submitted to the FDA as Expedited IND Safety Reports.

#### **7 Calendar-Day Telephone or Fax Report**

The Sponsor-Investigator is required to notify the FDA of a fatal or life-threatening adverse event that is unexpected and assessed by the investigator to be possibly related to the use of *investigational agents*. An unexpected adverse event is one that is not already described in the most recent Guidance for Investigator section of the Investigator's Brochure. Such reports are

to be telephoned or faxed to the FDA, Merck and Exelixis within 7 calendar days of the first learning of the event.

15 Calendar-Day Written Report

The Sponsor-Investigator is also required to notify the FDA and all participating investigators, in a written IND Safety Report, of any serious unexpected adverse event that is considered reasonably or possibly related to the use of investigational agent.

Written IND Safety Reports with analysis of similar events are to be submitted to the FDA, Exelixis, and Merck within 15 calendar days of first learning of the event. The FDA prefers these reports on a MedWatch 3500 Form but alternative formats (eg, summary letter) are acceptable.

FDA Fax number of IND Safety Reports: [name]

All written IND Safety Reports submitted to the FDA by the Sponsor-Investigator must also be faxed to:

Exelixis Drug Safety  
[contact]

Merck Global Safety  
[contact]

Table 6 Evaluating Adverse Events

An investigator who is a qualified physician, will evaluate all adverse events as to:

V4.0 CTCAE Grading	Grade 1	Mild; asymptomatic or mild symptoms; clinical or diagnostic observations only; intervention not indicated.
	Grade 2	Moderate; minimal, local or noninvasive intervention indicated; limiting age-appropriate instrumental ADL.
	Grade 3	Severe or medically significant but not immediately life-threatening; hospitalization or prolongation of hospitalization indicated; disabling; limiting self-care ADL.
	Grade 4	Life threatening consequences; urgent intervention indicated.
	Grade 5	Death related to AE
Seriousness	A serious adverse event is any adverse event occurring at any dose or during any use of investigational product that:	
	†Results in death; or	
	†Is life threatening; or places the subject, in the view of the investigator, at immediate risk of death from the event as it occurred (Note: This does not include an adverse event that, had it occurred in a more severe form, might have caused death.); or	
	†Results in a persistent or significant disability/incapacity (substantial disruption of one’s ability to conduct normal life functions); or	
	†Results in or prolongs an existing inpatient hospitalization (hospitalization is defined as an inpatient admission, regardless of length of stay, even if the hospitalization is a precautionary measure for continued observation. (Note: Hospitalization for an elective procedure to treat a pre-existing condition that has not worsened is not a serious adverse event. A pre-existing condition is a clinical condition that is diagnosed prior to the use of investigational products and is documented in the patient’s medical history.); or	
	†Is a congenital anomaly/birth defect (in offspring of subject taking the product regardless of time to diagnosis);or	
	Is a new cancer (that is not a condition of the study) (although not serious per ICH definition, is reportable to the Sponsor within 24 hours and to Merck and Exelixis within 2 working days to meet certain local requirements); or	
	Is an overdose (whether accidental or intentional). Any adverse event associated with an overdose is considered a serious adverse event for collection purposes. An overdose that is not associated with an adverse event is considered a non-serious event of clinical interest and must be reported within 24 hours to the Sponsor and to Merck and Exelixis within 2 working days.	

	Other important medical events that may not result in death, not be life threatening, or not require hospitalization may be considered a serious adverse event when, based upon appropriate medical judgment, the event may jeopardize the subject and may require medical or surgical intervention to prevent one of the outcomes listed previously (designated above by a †).	
Duration	Record the start and stop dates of the adverse event. If less than 1 day, indicate the appropriate length of time and units	
Action taken	Did the adverse event cause investigational products to be discontinued?	
Relationship to investigational Product(s)	
Did investigational product(s) cause the adverse event? The determination of the likelihood that investigational product(s) caused the adverse event will be provided by an investigator who is a qualified physician. The investigator's signed/dated initials on the source document or worksheet that supports the causality noted on the AE form, ensures that a medically qualified assessment of causality was done. This initialed document must be retained for the required regulatory time frame. The criteria below are intended as reference guidelines to assist the investigator in assessing the likelihood of a relationship between the test drug and the adverse event based upon the available information.
 
The following components are to be used to assess the relationship between investigational product and the AE; the greater the correlation with the components and their respective elements (in number and/or intensity), the more likely Merck product caused the adverse event (AE):
	
	Exposure	Is there evidence that the subject was actually exposed to investigational product(s) such as: reliable history, acceptable compliance assessment (pill count, diary, etc.), expected pharmacologic effect, or measurement of drug/metabolite in bodily specimen?
	Time Course	
Did the AE follow in a reasonable temporal sequence from administration of investigational product(s)?
 
Is the time of onset of the AE compatible with a drug-induced effect (applies to trials with investigational medicinal product)?

	Likely Cause	Is the AE not reasonably explained by another etiology such as underlying disease, other drug(s)/vaccine(s), or other host or environmental factors

Relationship to investigational product (continued)	The following components are to be used to assess the relationship between the test drug and the AE: (continued)	
	Dechallenge	
Was investigational product(s) discontinued or dose/exposure/frequency reduced?
 
If yes, did the AE resolve or improve?
 
If yes, this is a positive dechallenge. If no, this is a negative dechallenge.
 
(Note: This criterion is not applicable if: (1) the AE resulted in death or permanent disability; (2) the AE resolved/improved despite continuation of the Sponsor's product; or (3) the trial is a single-dose drug trial); or (4) Sponsor's product(s) is/are only used one time.)

	Rechallenge	
Was the subject re-exposed to investigational product(s) in this study?
 
If yes, did the AE recur or worsen?
 
If yes, this is a positive rechallenge. If no, this is a negative rechallenge.
 
(Note: This criterion is not applicable if: (1) the initial AE resulted in death or permanent disability, or (2) the trial is a single-dose drug trial); or (3) Sponsor's product(s) is/are used only one time).
 
NOTE: IF A RECHALLENGE IS PLANNED FOR AN ADVERSE EVENT WHICH WAS SERIOUS AND WHICH MAY HAVE BEEN CAUSED BY investigational PRODUCT, OR IF REEXPOSURE TO MERCK PRODUCT POSES ADDITIONAL POTENTIAL SIGNIFICANT RISK TO THE SUBJECT, THEN THE RECHALLENGE MUST BE APPROVED IN ADVANCE BY THE SPONSOR AS PER DOSE MODIFICATION GUIDELINES IN THE PROTOCOL.

	Consistency with Trial Treatment Profile	
Is the clinical/pathological presentation of the AE consistent with previous knowledge regarding investigational product(s) or drug class pharmacology or toxicology?

The assessment of relationship will be reported on the case report forms /worksheets by an investigator who is a qualified physician according to his/her best clinical judgment, including consideration of the above elements.
		
Record one of the following	Use the following scale of criteria as guidance (not all criteria must be present to be indicative of investigational product(s) relationship).	
Yes, there is a reasonable possibility of investigational product(s) relationship.	
There is evidence of exposure to investigational product (s) . The temporal sequence of the AE onset relative to the administration of investigational product(s) is reasonable. The AE is more likely explained by investigational product(s) than by another cause.
	
No, there is not a reasonable possibility of investigational product(s) relationship	
Subject did not receive the investigational product OR temporal sequence of the AE onset relative to administration of investigational product(s) is not reasonable OR the AE is more likely explained by another cause than the Merck product. (Also entered for a subject with overdose without an associated AE.)
	

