### **5.3 Dose Modification:**

XL 888 and pembrolizumab have class-specific safety profiles based on their mechanism of action but may also cause AEs that overlap. For management of AEs which can be clearly attributed to XL 888 or pembrolizumab, independent dose modification for either agent is allowed. For AEs without clear attribution to either study treatment, management of toxicity should include dose modifications of both agents.

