## **7.2 Assessing and Recording Adverse Events**

An adverse event is defined as any untoward medical occurrence in a patient or clinical investigation subject administered a pharmaceutical product and which does not necessarily have to have a causal relationship with this treatment. An adverse event can therefore be any unfavorable and unintended sign (including an abnormal laboratory finding, for example), symptom, or disease temporally associated with the use of a medicinal product or protocol-specified procedure, whether or not considered related to the medicinal product or protocol-specified procedure. Any worsening (i.e., any clinically significant adverse change in

frequency and/or intensity) of a preexisting condition that is temporally associated with the use of the investigational products, is also an adverse event.

Changes resulting from normal growth and development that do not vary significantly in frequency or severity from expected levels are not to be considered adverse events. Examples of this may include, but are not limited to, teething, typical crying in infants and children and onset of menses or menopause occurring at a physiologically appropriate time.

Investigational products include pembrolizumab and XL888.

Adverse events may occur during the course of the use of investigational products in clinical trials, or as prescribed in clinical practice, from overdose (whether accidental or intentional), from abuse and from withdrawal.

All adverse events that occur after the consent form is signed but before treatment allocation/randomization must be reported by the investigator if they cause the subject to be excluded from the trial, or are the result of a protocol-specified intervention, including but not limited to washout or discontinuation of usual therapy, diet, placebo treatment or a procedure.

From the time of treatment allocation/randomization through 30 days following cessation of treatment, all adverse events must be reported by the investigator. Such events will be recorded at each examination on the Adverse Event case report forms/worksheets. The reporting timeframe for adverse events meeting any serious criteria is described in section 7.2.4. The investigator will make every attempt to follow all subjects with non-serious adverse events for outcome.

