### **8.6 Safety Analysis**

#### **8.6.1.1 Adverse Events**

Adverse events will be classified using MedDRA System Organ Classes and Preferred Terms. Furthermore, SAEs, AEs with a severity grade of 3 or above using NCI CTCAE version 4.0, AEs deemed related to study drug, AEs leading to discontinuation of study drug, and AEs leading to death will also be summarized in preferred term by system organ class and listed on an individual subject basis.

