## 9.0 LABELING, PACKAGING, STORAGE AND RETURN OF CLINICAL SUPPLIES

### 9.1 Investigational Product

#### 9.1.1 Pembrolizumab

The investigator shall take responsibility for and shall take all steps to maintain appropriate records and ensure appropriate supply, storage, handling, distribution and usage of investigational product in accordance with the protocol and any applicable laws and regulations.

Clinical Supplies will be provided by Merck as summarized in Table 7.

Table 7 Product Descriptions

Product Name & Potency	Dosage Form
Pembrolizumab 50 mg	Lyophilized Powder for Injection
Pembrolizumab 100 mg/ 4mL	Solution for Injection

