### **9.1.2 Returns and Reconciliation**

The investigator is responsible for keeping accurate records of the clinical supplies received from Exelixis, the amount dispensed to and returned by the subjects and the amount remaining at the conclusion of the trial.

Upon completion or termination of the study, all unused and/or partially used investigational product will be destroyed at the site per institutional policy. It is the Investigator's responsibility to arrange for disposal of all empty containers, provided that procedures for proper disposal have been established according to applicable federal, state, local and institutional guidelines and procedures, and provided that appropriate records of disposal are kept.

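### Table 6 asks about both drugs but words parts of its causality test for the Merck product alone, so an event caused only by XL888 fits both Yes and No

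*Combined protocol and SAP*

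**What the plan says.** Section 7.2 sets the scope: "Investigational products include pembrolizumab and XL888". Table 6 in section 7.3 then tells a qualified physician how to judge causality and to record one of two answers, Yes or No.

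The Yes row covers both drugs: "The AE is more likely explained by investigational product(s) than by another cause". The No row has three limbs joined by OR, so any one is enough. The third applies when "the AE is more likely explained by another cause than the Merck product". The sentence that introduces the assessment components has the same narrow scope: the better the fit, "the more likely Merck product caused the adverse event (AE". The capitalised note on rechallenge refers to the investigational product in its first limb and to the Merck product in its second. The small-print notes under dechallenge and rechallenge use a third term, the Sponsor's product.

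Three other sections depend on attribution:
- Section 5.3 says that, where an event can be clearly attributed to one drug, "independent dose modification for either agent is allowed". Section 5.3.2 relies on the investigator attributing toxicity to XL888 in particular.
- Section 5.2.3 counts an event as a DLT only if it is definitely treatment related. It does not cite Table 6.
- Section 8.6.1.1 summarises "AEs deemed related to study drug".

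**The concern.** XL888 is the drug whose dose is escalated. Pembrolizumab is fixed at 200 mg. The toxicity that should rise with dose level is therefore XL888 toxicity, and that is the toxicity the narrow wording leaves out. If XL888 counts as another cause relative to the Merck product, an event due to XL888 alone meets a sufficient condition for No.

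Any resulting error runs one way, because the narrow wording can only remove XL888 events from the related category. The related-event summary would be understated. If the same answer were carried into DLT adjudication, a dose level could pass too easily. Expedited reporting under section 7.3 also depends on possible relation to the investigational agents.

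Separately, Table 6 describes one combined answer, while sections 5.3 and 5.3.2 need an answer for each drug.

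**Working it through.** The plan states no figure on this point, so there is none to reproduce. The check is mainly a comparison of texts.

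**Step 1: which drug is the Merck product.** Section 9.1.1, on pembrolizumab, says "Clinical Supplies will be provided by Merck as summarized in Table 7". The returns paragraph under section 9.2, on XL888, speaks of "the clinical supplies received from Exelixis". The Merck product is therefore pembrolizumab, and XL888 is not a Merck product.

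**Step 2: scope of each element of Table 6.**

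| Element | Product named |
|---|---|
| Lead question, exposure, time course, consistency | Investigational product(s) |
| Dechallenge and rechallenge questions | Investigational product(s) |
| Notes under dechallenge and rechallenge | Sponsor's product |
| Lead-in to the components | Merck product |
| Capitalised rechallenge note, second limb | Merck product |
| Yes row | Investigational product(s) |
| Heading of the No row | Investigational product(s) |
| No row, third limb | Merck product |

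**Step 3: apply the table to an event caused by XL888 and not by pembrolizumab.**
- Yes row: an investigational product explains the event better than any other cause. Satisfied.
- No row, third limb: XL888 is a cause other than the Merck product and explains the event better. Satisfied.
- The likely-cause component lists other drugs among the alternative explanations, which does nothing to exclude this reading.

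Both rows apply, and the physician must record one. The table contradicts itself for this class of event.

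**Step 4: follow the recorded answer.** The relationship is entered on the case report forms or worksheets. The related-event summary in 8.6.1.1 needs a recorded relationship, and Table 6 is the only scale offered, so this link is close, though not stated. The link to DLTs is weaker. Section 5.2.3 has its own threshold, and a Yes/No scale has no level that corresponds to definitely.

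**Step 5: illustration of the DLT route.** Let p be the true DLT rate at a dose level and m the share of true DLTs recorded as unrelated. Both are assumptions; the documents give neither. The counted rate is q = p(1 − m). Under sections 5.2.2 and 8.1 a level fails with two or more DLTs in 3 or 6 patients. It passes with 0 of 3, or with 1 of 3 followed by 0 of 3:

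P(pass) = (1 − q)³ + 3q(1 − q)² × (1 − q)³ = (1 − q)³ + 3q(1 − q)⁵

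For p = 0.40:
- m = 0, q = 0.40: 0.2160 + 0.0933 = 0.309
- m = 0.25, q = 0.30: 0.3430 + 0.1513 = 0.494
- m = 0.50, q = 0.20: 0.5120 + 0.1966 = 0.709

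| True rate p | m = 0 | m = 0.10 | m = 0.25 | m = 0.50 |
|---|---|---|---|---|
| 0.33 | 0.434 | 0.500 | 0.605 | 0.783 |
| 0.40 | 0.309 | 0.378 | 0.494 | 0.709 |
| 0.50 | 0.172 | 0.234 | 0.351 | 0.600 |

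The table shows direction and sensitivity. It does not estimate what happens in this trial.

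**The case against.** The strongest reply is that this is a slip of wording which a competent physician would read past. The lead question, most of the component questions, the Yes row and the heading of the No row all refer to the investigational products, and section 7.2 puts XL888 among them. A physician who blames XL888 cannot truthfully tick an answer whose heading denies a relationship to the investigational products. The exposure component mentions pill counts and a diary, which in this trial fit only oral XL888 (section 7.1.1.6), so the table was evidently meant to cover it. The criteria are offered as guidance for clinical judgment and are not a mechanical score. All of this stands. A reader might infer that the form classes XL888 events as unrelated outright, and the documents do not support that.

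A reader might also infer that such events drop out of the DLT count. That does not follow either. Section 5.2.3 sets its own standard without reference to Table 6, and one of its criteria names XL888 directly. Section 5.3.2.2 lists visual, hepatic, gastrointestinal and QTc effects as XL888 toxicities. The DSMC sees the safety data for a dose level before approving escalation.

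The wider safety report is partly protected too. Section 8.6.1.1 also summarises serious events, events of grade 3 or above, and events leading to discontinuation or death, whatever their relationship, and section 8.3 reports worst toxicity per patient.

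What the reply does not remove is the contradiction. A sufficient limb of No still points the wrong way for the escalated drug, and guidance does not help when it supports both answers. Sections 5.3 and 5.3.2 do expect attribution to each drug, but Table 6 gives no place to record it. The case report form is not among the documents and may already have one.

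**Conclusion.** The point holds as an internal contradiction in the only causality scale that the documents provide. Read literally, an event due to XL888 alone satisfies both Yes and No and could be recorded as unrelated. The consequence closest to hand is an understated related-event summary under 8.6.1.1. This rests on the reasonable but unstated assumption that the summary draws on the Table 6 answer.

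An effect on DLT attribution is possible and remains an inference. The 3+3 probabilities depend on an assumed DLT rate and an assumed miscoding share. Nothing in the documents shows that miscoding would occur or how often, so a rise from 0.309 to 0.494 or 0.709 must not be quoted as the expected harm. No sample size or error rate in the plan changes.

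This is a minor-to-moderate correction. It is worth making because the ambiguity concerns the escalated drug, can bias in one direction only, and costs almost nothing to remove.

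**What to change.** 1. In Table 6, replace Merck product and Sponsor's product with investigational product(s) (pembrolizumab and/or XL888) in the lead-in, the third limb of the No row, and the dechallenge and rechallenge text. For the rechallenge approval note this aligns the terms only; the protocol's authors must reconcile which products its two limbs cover.
2. Record relationship separately for pembrolizumab and for XL888, as sections 5.3 and 5.3.2 already presuppose.
3. State that an event is related for 8.6.1.1 if either answer is Yes.
4. State how the Yes/No scale corresponds to the definitely-related threshold in 5.2.3, so that DLT adjudication and the related-event summary rest on a stated common basis.

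The cost is protocol wording and, if the case report form does not already capture it, one extra field. Related-event percentages may rise slightly.
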